2.3 Safety Data Summary of Figures and Tables

Adverse events will be listed.

	Title: UCC-23AC023 Statistical Analysis Plan Table shells	Page No.
	25 of 33	
	Study Title: UCC-23AC023 PureWick Adolescent Study	Version No:
	CIP/CPSP Version: 1.0	1.0

Template GFM-10082B

3.0 SHELLS AND SPECIFICATIONS FOR LISTINGS

3.1 Subject Data Listings

3.1.1 Screen Failure

Listing 1 Screen Failures

Enrolled

Subject ID	Eligibility criteria not met

3.1.2 Enrollment details

Listing 2 Randomization and Treatment Status

Enrolled

Subject ID	Eligibility Met	Randomized?	Date of Randomization	Randomization No.	Randomized Sequence
		Yes			
		No			

Listing 3 End of Study Status

ITT

Subject ID	Date of Study Completion/Discontinuation	Status	Other, Specify	Date of death	Primary cause of death

	Title: UCC-23AC023 Statistical Analysis Plan Table shells 3.1.3 Protocol Deviations	Page No. 26 of 33
	Study Title: UCC-23AC023 PureWick Adolescent Study CIP/CPSP Version: 1.0	Version No: 1.0

Template GFM-10082B

Listing 4 Protocol Deviations

ITT

Subject ID	Date of Deviation	Nature of Deviation	Additional Details	Major Protocol Deviation

3.1.4 Patients excluded from the Efficacy Analysis

Listing 5 Voids did not meet Evaluable Criteria

ITT

Subject ID	Void	Device Placed By	Device	Did the Participant Have a Void	Pad Starting Weight (g)	Pad Final Weight (g)	Canister Starting Weight (g)	Canister Final Weight (g)

	Title: UCC-23AC023 Statistical Analysis Plan Table shells	Page No.
	27 of 33	
	Study Title: UCC-23AC023 PureWick Adolescent Study	Version No:
	CIP/CPSP Version: 1.0	1.0

Template GFM-10082B

3.1.6 Individual Efficacy Response data

Listing 7 Treatment Details (Part 1)

ITT

Subject ID	Void	Was Device Placed	Device Placed by	Device	Did Participant Have a Void	Signs of Irritation Prior (If yes, specify)	Signs of Irritation After (If yes, specify)	Did the Catheter Move/Dislodged	Any Leakage Observed by HCP
	Void 1	Yes	HCP						
	Void 2	Yes	SelfPlaced						

	Title: UCC-23AC023 Statistical Analysis Plan Table shells	Page No.
	28 of 33	
	Study Title: UCC-23AC023 PureWick Adolescent Study	Version No:
	CIP/CPSP Version: 1.0	1.0

Template GFM-10082B

Listing 8 Treatment Details (Part 2)

ITT

Subject ID	Void	Was Device Placed	Device Placed by	Device	Did Subject Participate in Device Placement/Void Attempt	Did the Guardian/Parent Help the Participant Place the Device	Was the Device Correctly Connected to Canister via Collector Tubing (If No, Reason; If Other, Specify)	Did HCP Feel the Catheter was Correctly Placed	Was Catheter Repositioned by Participant After Placement
	Void 1	Yes	HCP						
	Void 2	Yes	SelfPlaced						

	Title: UCC-23AC023 Statistical Analysis Plan Table shells	Page No.
	29 of 33	
	Study Title: UCC-23AC023 PureWick Adolescent Study	Version No:
	CIP/CPSP Version: 1.0	1.0

Template GFM-10082B

Listing 9 Treatment Details (Part 3)

ITT

Subject ID	Void	Was Device Placed	Device Placed by	Device	Pad Starting Weight (g)	Pad Final Weight (g)	Canister Starting Weight (g)	Canister Final Weight (g)
	Void 1							
	Void 2							

Listing 10 Capture Rate

ITT

Subject ID	Void	Device Placed by	Device	Leaked Weight (g)	Captured Weight (g)	Void Weight (g)	Evaluable	Capture Rate (%)
	Void 1						Yes	
	Void 2						No	N/A, Not Evaluable

	Title: UCC-23AC023 Statistical Analysis Plan Table shells	Page No.
	30 of 33	
	Study Title: UCC-23AC023 PureWick Adolescent Study	Version No:
	CIP/CPSP Version: 1.0	1.0

Template GFM-10082B

Listing 11 Participant - Perception of Wetness

ITT

Subject ID	Void	Device	Void Type	Questionnaire Completed	How Wet or Dry did You Feel After Your Urination	Comments if selected 1/2/3	Did you Feel Leakage While Voiding
	Void 1				1-Extremely Wet		Yes
	Void 2						

Listing 12 Participant Ease of Use – Both Device

ITT

Subject ID	Questionnaire Completed	Device	How Easy was the Placement of the Device	How Easy was the Removal of the Device
		PureWick Flex Female	1-Very Difficult	
		PureWick Male		

	Title: UCC-23AC023 Statistical Analysis Plan Table shells	Page No.
	31 of 33	
	Study Title: UCC-23AC023 PureWick Adolescent Study	Version No:
	CIP/CPSP Version: 1.0	1.0

Template GFM-10082B

Listing 13 Participant Ease of Use – PureWick Flex Female only

ITT

Subject ID	Able to Connect the Device Tubing (If 1/2/3, comments)	Able to Locate the Vent Hole (If 1/2/3, comments)	Able to Tell if Came Out of Place (If 1/2/3, comments)	Able to Tell if in Correct Orientation (If 1/2/3, comments)	Able to Curve to Fit (If 1/2/3, comments)
	1- Strongly Disagree (xxxxx)				

Listing 14 HCP Ease of Use

ITT

HCP Initials	Questionnaire Completed	Device	How Easy was the Placement of the Device	How Easy was the Removal of the Device
		PureWick Flex Female	1-Very Difficult	5-Very Easy
		PureWick Male		

	Title: UCC-23AC023 Statistical Analysis Plan Table shells	Page No.
	32 of 33	
	Study Title: UCC-23AC023 PureWick Adolescent Study	Version No:
	CIP/CPSP Version: 1.0	1.0

Template GFM-10082B

Listing 15 Participant IFU

ITT

Subject ID	Questionnaire Completed	Device	Able to Understand Written Instructions (If 1/2/3, comments)	Able to Understand Pictures Instructions (If 1/2/3, comments)	Able to Place on Myself (If 1/2/3, comments)
		PureWick Flex Female	1-Strongly Disagree (xxxxxx)		
		PureWick Male			

Listing 16 Participant Comfort Scale Survey

ITT

Subject ID	Questionnaire Completed	Device	How Comfortable was the Placement	How Comfortable was the device while voiding	How Comfortable was the Removal	How Likely to Recommend
			2-Uncomfortable	1-Very Uncomfortable	5-Very Comfortable	4-Likely

	Title: UCC-23AC023 Statistical Analysis Plan Table shells	Page No. 33 of 33
	Study Title: UCC-23AC023 PureWick Adolescent Study 3.1.8 Adverse Event Listing (each subject) CIP/CPSP Version: 1.0	Version No: 1.0

Template GFM-10082B

Listing 17 Adverse Events

ITT

Subject ID	AE(Reported)/SOC/PT	Start Date / End Date	Outcome of AE	Severity	Relation to Study Device	Relation to Procedure	SAE	UADE	Additional Details
					Yes/xxx	Yes/xxx		Yes/No	
					No				

Listing 18 Serious Adverse Events

ITT

Subject ID	AE(Reported)/SOC/PT	Start Date	Result in Death	Life Threatening or Injury	If Require or Prolongs Hospitalization		Permanent Impairment of a Body Structure or Function	Necessitates Medical or Surgical Intervention	Fetal Distress, Fetal Death, Congenital Anomaly or Birth Defect	Meet Definition of Serious Health Threat
					Admission Date	Discharge Date				

	Title: UCC-23AC023 Statistical Analysis Plan Table shells	Page No. 34 of 33
	Study Title: UCC-23AC023 PureWick Adolescent Study CIP/CPSP Version: 1.0	Version No: 1.0

Template GFM-10082B

3.1.9 Device Deficiency

Listing 19 Device Deficiencies

ITT

Subject ID	Date of Device Deficiencies	Time of Device Deficiencies	Device Name/identifier	Failure Code	Details	Additional Details	Lot Number	Device Used to Treat Subject	AE Associated with Device Deficiencies	Could the Device Deficiency Meet SADE	Meet Definition of Serious Health Threat
	DDMMYY YY							Yes/No	Yes/No		

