5.0 IDENTIFICATION AND DESCRIPTION OF THE STUDY DEVICE

5.1 Study Device(s) and Comparator(s)

Study participants will be evaluating the PureWick™ Male External Catheter (male participants) or the PureWick™ Flex Female External Catheter (female participants). Both study devices will be used with the PureWick™ Urine Collection System, a 510(k) exempt device currently marketed in the United States. All study devices will have a lot number for product traceability.

PureWick™ Male External Catheter

The PureWick™ Male External Catheter (Figure 1) is intended for non-invasive urine output management in users with male anatomy. This device is a Class I, 510k exempt device which is marketed in the United States. The device Instructions for Use (IFU) can be found in Appendix 1. Male participants will void two times using the PureWick™ MEC. The study will utilize approximately 40 PureWick™ MECs, 2 per male participant.

[figure not shown]

Figure 1

 BD	Document Type: Global Clinical	Page No: 7 of 59
	Title: Clinical Investigation Plan Study ID: UCC-23AC023	Version No: 1.0

Template GFM-10095B

PureWick™ Flex Female External Catheter

The PureWick™ Flex Female External Catheter is intended for non-invasive urine output management in adult users with female anatomy. The PureWick™ Flex FEC (Figure 2) is a non-sterile single use device. The device is a flexible, contoured external catheter (a "Wick") that is positioned between the separated gluteus and labia, against the urethra. The wick is connected to the free-standing PureWick™ Urine Collection System (PUCS) via tubing. The PUCS uses suction (not felt by the user) to pull voided urine through the wick, regardless of the urine flow rate. Urine continues quickly through PVC tubing, away from the body until it reaches the collection canister.

The PureWick™ Flex FEC is currently on the market. The device is composed of silicone, polyester non-woven foam, bamboo mid-layer sheet, polypropylene top sheet, PVC dual lumen tubing; all materials common in medical devices. The device also consists of an aluminum wire inside of the dual lumen PVC tubing that allows the FEC to hold its shape when formed.

The device Instructions for Use (IFU) can be found in Appendix 2. Female participants will void two times using the PureWick™ Flex FEC. The study will utilize approximately 40 PureWick™ Flex FECs, 2 per female participant.

THE PRODUCT

[figure not shown]

Figure 2

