9.5.1 Replacement of Subjects

	Document Type: Global Clinical Title: Clinical Investigation Plan Study ID: UCC-23AC023	Page No: 15 of 59
		Version No: 1.0

Template GFM-10095B

Not Applicable – This study will not have replacement participants.

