11.2 Analysis Population

The analysis populations will be defined as follows for this study:

Population	Description
Enrolled	All participants who sign the ICF
Intent-to-Treat (ITT)	All participants who have device placed for at least one void.
Per-Protocol (PP)	ITT subjects without any major protocol deviations

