19.1.7 Device Deficiency

A device deficiency is defined as inadequacy of a medical device with respect to its identity, quality, durability, reliability, usability, safety or performance. Device deficiencies include malfunctions, use errors, and inadequacy in the information supplied by the manufacturer including labelling. This definition includes device deficiencies related to the investigational medical device or the comparator.

This applies to: devices used to treat the subject, or devices in which the package was opened, but the device was not used for treatment, or devices with which treatment was attempted, but the device did not remain through the entire study procedure/period.

	Document Type: Global Clinical	Page No: 26 of 59
	Title: Clinical Investigation Plan Study ID: UCC-23AC023	Version No: 1.0

Template GFM-10095B

The Principal Investigator will record all device deficiencies for both the study device and the comparator, if the comparator is a medical device, on the appropriate CRF. Device deficiencies will be reported to the Sponsor.

If the device deficiency was associated with an AE, the reporting provisions for AEs, ADEs, SAEs, SADEs and UADEs/USADEs apply.

It is the responsibility of the Investigator to notify the IRB/EC of such device deficiencies in accordance with the IRB/EC and/or the Competent Authority's local regulations.

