19.3.1 Report by Investigator to Sponsor and IRB/EC

For all adverse events, all sections of the appropriate Case Report Form (CRF) must be completed.

- All SAEs, SADEs, UADEs/USADEs, and Serious Health Threats must be reported to the Sponsor no later than 1 calendar days of the clinical site/investigator becoming aware of the event.
- All AEs must be reported to the Sponsor no later than 1 calendar days.
- All device deficiencies must be report to the Sponsor no later than 1 calendar days.
- De-identified copies of all requested relevant documentation should be submitted to the Sponsor within 72 hours of the Sponsor's request.
- The Principal Investigator must report adverse events to individual Institutional Review Boards (IRBs)/Ethics Committees (ECs) per the IRB/EC requirements.

	Document Type: Global Clinical	Page No: 29 of 59
	Title: Clinical Investigation Plan Study ID: UCC-23AC023	Version No: 1.0

Template GFM-10095B

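### Listing 19, the only device-deficiency output in the visible SAP shells, is restricted to ITT, so deficiencies in participants who never had a device placed, or not linked to an ITT participant, are not reported

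*SAP*

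**What the plan says.** - **Definition.** Protocol section 19.1.7 covers inadequacies in quality, reliability, usability and performance, and includes malfunctions and use errors. It applies to devices used, to "devices in which the package was opened, but the device was not used for treatment", and to devices with which treatment was attempted but which did not stay on throughout.
- **Recording and reporting.** The same section says: "The Principal Investigator will record all device deficiencies for both the study device and the comparator". Section 19.3.1 adds: "All device deficiencies must be report to the Sponsor no later than 1 calendar days". Neither duty is tied to an analysis population.
- **Populations.** Protocol section 11.2 defines Enrolled as "All participants who sign the ICF" and ITT as "All participants who have device placed for at least one void".
- **Output.** SAP section 3.1.9 contains "Listing 19 Device Deficiencies" with the population line ITT. It has a Yes/No column for whether the device was used to treat the subject. No other shell covers deficiencies. SAP section 2.3 provides only for listing adverse events, and Protocol section 11.4.4 rules out analyses beyond the SAP.

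**The concern.** The listing's population is narrower than the definition of what it lists. Entry to ITT requires that a device was placed at least once, while the protocol deliberately counts devices that were opened and never used. The listing's own Yes/No column shows that rows for unused devices are expected, yet the ITT filter removes those rows for any participant who never got a device on.

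The study is meant to support an expanded indication (Protocol section 7.2) and asks whether adolescents can use the device alone or with help (section 4.2). A participant for whom no device could be placed is the most complete failure the study could observe. With 20 participants per device, one omitted case could turn a listing with an entry into one with none.

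**Working it through.** The plan states no figure to reproduce on this point. The check sets the passages side by side and follows a deficiency through the planned outputs.

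1. **Can a deficiency arise before ITT entry?** Yes. In Protocol section 10.4, set-up and checking of the collection system (step 1.4), shaping of the female device (2.2) and tubing connection (2.3) all come before placement (2.4).

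2. **Which deficiencies does the filter keep or drop?** ITT is a property of the participant, and each participant has two planned placements, with a new device for the second.
   - Device fails before placement, and the participant has a device placed at the same void or the other one: in ITT, deficiency listed, with the used-to-treat column marked No.
   - Device fails before placement, and the participant has no device placed at either void: not in ITT, deficiency not listed.
   - Deficiency not linked to an ITT participant: not listed.

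3. **Does another output show the dropped cases?** Not the deficiency itself. Tables 5 to 7 and Listings 3, 4 and 7 to 9 are also ITT. Among the Enrolled outputs, Table 2 would show a gap between the Enrolled and ITT counts, Listing 2 would show the participant as randomized, and Table 1 could show a discontinuation. The reasons in Table 1 have no device-deficiency category, so the cause would not be visible.

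4. **Can the loss be sized?** Only under assumptions. Let p be the chance that a failure prevents a given placement, with N = 40 participants. The documents give no p, so 1% to 10% is assumed purely to show the spread.
   - If void 2 is always attempted and failures are independent, expected failures are 2Np and those lost are 2Np², a share of p. At p = 5%: 80 × 0.05 = 4.0 expected, 80 × 0.0025 = 0.2 lost, or 5%. The share is 1% at p = 1% and 10% at p = 10%.
   - If a void 1 failure always ends participation, expected failures are Np + N(1 − p)p and those lost are Np. At p = 5%: 2.0 + 1.9 = 3.9 expected, 2.0 lost, or 51%. The share is 50% at p = 1% and 53% at p = 10%.

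   The answer runs from about 1% to about half, depending mainly on what happens after a failed placement. The documents do not say, so neither figure is an estimate for this study.

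**The case against.** A reader might infer that every failure preventing placement disappears from the results. The documents do not support that: as step 2 shows, such a failure stays listed whenever the same participant had any device placed.

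A reader might also infer that a failed catheter ends participation, from "This study will not have replacement participants" and "The study will utilize approximately 40 PureWick™ MECs, 2 per male participant". The first concerns replacing participants and says nothing about swapping a device. The second is an approximate count. Section 5.1.1 says the devices are commercially available, and section 13.0 provides for return of unused devices at close-out, so surplus stock is contemplated. Step 1.4 has the HCP adjust the collection system before going on, so a pump fault need not stop a participant either.

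Nor are the excluded deficiencies lost to oversight. They are recorded on the CRF and reported to the sponsor within one calendar day, and Tables 1 and 2 let a reader count participants who left before placement.

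The ITT label may simply be a default. Listing 14, which has one row per HCP and device, is also labelled ITT, while Table 14 on the same questionnaire is labelled HCP.

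All of this stands, and it makes the gap small. It does not close it: as written, the listing still excludes deficiencies that the protocol says must be recorded, and no other visible shell carries their detail.

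**Conclusion.** The mismatch is real and narrow. Deficiencies in participants with no device placed at either void, and any not linked to an ITT participant, fall outside the only deficiency output in the visible shells. The omission affects the reported results, not data capture. Its direction is known, since widening the population can only add rows. Its size is not known, because the documents give neither a failure rate nor a rule for what follows a failed placement. It could well be zero rows in a study of 40 healthy volunteers.

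The conclusion assumes that the ITT line will be applied literally, and that the published shells are the full set of planned deficiency outputs. Severity: minor.

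**What to change.** In SAP section 3.1.9, change the population line of Listing 19 from ITT to: *Enrolled (all recorded device deficiencies, whether or not a device was placed)*. The words in parentheses matter, because they also bring in a deficiency with no participant attached. The subject column can then show N/A, which SAP section 1.3 already allows for missing entries in listings.

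The cost is one line in the SAP. The deficiencies are already recorded on the CRF, the column separating used from unused devices already exists, and no table or analysis changes. The listing may become slightly longer, and so slightly less favourable to the device.

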4.0 REFERENCES

N/A

